12.2 Follow-up data collection

12.2.1 Pupil and teacher self-report questionnaires

At Month 12 follow-up KS2 pupils and teachers will complete the same questionnaires in the same method as described in Section 9.1.4. In addition, parent/carers will also complete the CSRI [34] which will provide data to be used in the health economics evaluation.

12.2.2 Linkage to routinely collected data

The Trial Manager will request access to the NPD close to the 12-month follow-up (data release dependent). This will include KS2 Attainment, Absence and Exclusions datasets. Participant identifiers (pupil name and date of birth) will be sent to the Department for Education using their secure data transfer system. Trial data will be linked to the NPD database. Identifiers will be removed, and researchers will access the linked data via a data safe haven.

Parents will also be asked to consent to be contacted by researchers in the future if there is a request to link children's trial data with other data.

12.2.3 Usual antibullying practice

At Month 12 follow-up, data on schools' usual antibullying practices will be obtained using the same method as described in Section 9.1.3. In addition, interviews will be conducted with teachers from three control schools. Interviews will be audio recorded and transcripts will be anonymised.

12.2.4 Process evaluation

12.2.4.1 KiVa implementation fidelity

Teachers in KiVa schools will complete an online or paper-based Teacher Lesson Record Books after each KiVa lesson. All intervention schools will complete a checklist to assess adherence to the schoolwide KiVa elements. Research assistants will observe intervention delivery in a purposively sampled group of 16 intervention schools. For these schools, research assistants will also complete the Lesson Record book and schoolwide checklist to assess reliability of teacher-reported lesson and schoolwide implementation fidelity.

12.2.4.2 Factors influencing KiVa implementation

Research assistants will conduct in-depth interviews with teachers involved with KiVa delivery from eight intervention schools around February/March 2021. These interviews will explore key factors influencing implementation of KiVA and how this varies across different school contexts.

12.2.4.3 KiVa intervention mechanisms

Research assistants will conduct focus groups with pupils and interviews with parents/carers of eight intervention schools around February/March 2021. Researchers will also observe class lessons and report on school-wide delivery and implementation of indicated actions. These data will enable us to understand: the extent to which key components of the intervention operate as intended; any unintended mechanisms; and ways in which KiVA interacts with school systems.

12.2.4.4 Usual antibullying practices

At Baseline, researchers will obtain a copy of each school's bullying policy either online or from the Headteacher. At Baseline and Month 12 follow-up, a trial specific proforma will be completed to identify what antibullying elements are in place at the school. Researchers will also obtain information through interviews with Headteachers.

13 Safety reporting

As SAEs have not been observed in previous trials implementing the KiVa programme, we do not plan to report SAE data in the current trial. A trial specific safeguarding procedure has been developed and details the procedures to be followed if a risk of harm to a child is disclosed or suspected. All field workers who visit schools will have enhanced DBS checks and will receive appropriate training. The name and contact details of each school's safeguarding lead will be documented at Baseline. Pupils will also be informed that if they disclose to a researcher information that causes concern about their health or safety, confidentiality may need to be broken to inform the school's safeguarding lead. All instances of reporting to the school will be documented in the TMF.

Table 1. Schedule of trial procedures.

Procedures	Time point			
	Screening/baseline	Pre-trial set-up	Trial period	Month 12
	(Feb-Apr 2020)	(May-June	(Sep 20-Jun	follow-up
		2020)	2021)	(Apr-Jun2021)
Eligibility assessment	x			
Informed	x			× ×
consent/assent				X
Demographic data	x			
collection				
Usual antibullying	x			×
practices				X
Randomisation		x		
KiVa training and		×		
school trial training		X		
Delivery of				
intervention/control			×	
condition				
Pupil and teacher				
questionnaire data	x			x
collection				
Linkage to routinely				x
collected data				^
Focus				x
groups/interviews				

14 Statistical considerations

14.1 Randomisation

Cluster (schools) will be randomised in a 1:1 ratio to receive either the KiVa intervention or usual practice. Within each of the four study areas (North Wales and Cheshire, West Midlands, South East England, South West England), schools will be stratified on their size (number of KS2 students (years 3-6)) and the percentage of students eligible for FSM to ensure balance across arms on parental socioeconomic disadvantage. Randomisation of schools will occur after all schools within area and strata have been recruited and they will be informed of their allocation after baseline data have been collected. All schools will be assigned a site ID number, after which an independent CTR statistician, will randomly allocate recruited schools to Intervention or Control using computer generated random number block allocations. The independent CTU statistician will allocate KiVa or Usual practice to ID numbers and inform the designated intervention delivery team member in each area.

14.2 Blinding

Baseline data collection which will occur prior to randomisation. It is not possible for KiVA study participants (students), teachers, Trial Managers, the intervention delivery team or researchers involved in the process evaluation to be blind to intervention status. While it is intended that Month 12 follow-up data collection will be conducted blinded, researchers and field workers may be unblinded to randomisation as schoolwide components of the KiVa intervention may be visible e.g. KiVa posters and vests. The statistician analysing the primary and secondary outcome data and the health economists undertaking the economic analysis will remain blinded. Potential risks of the intervention to participants are minimal but in the case where unblinding is necessary, the allocation schedule will be available to the researchers either electronically via the independent CTR statistician's copy.

14.3 Sample size

The sample size calculation is based on data from the roll-out of KiVa in Finland where a reduction from 18% to 14% in rates of victimisation was observed [37]. A similar baseline rate of victimisation of 18% was obtained from a current UK based pre-post study of 41 schools [23]. An individual pupil level analysis correcting for clustering by school will be undertaken. To achieve a reduction from 18% at baseline to 14% (4% absolute reduction, 22% relative reduction), a total of 3,520 pupils are required to power an

individual level trial at 90% and a 5% significance level. This reduction equates to an effect size (odds ratio) of 1.35 which is of public health significance and is broadly in line with other effect estimates from KiVa and the wider literature on bullying and victimisation. The pooled odds ratio found in Ttofi's and Farrington's 2018 systematic review of bullying and victimization was 1.24 [6] and our effect size is midrange of other relevant KiVa studies which range from 1.22 [11] to 1.47 [8]. The study will take account of clustering. In the Finnish study the school level intra-cluster correlation (ICC) for the comparison of KiVa and UP in self-reported victimization was 0.02 at the 12-month follow-up. An average cluster size of 111 pupils in years 3 to 5 is assumed. This is based on recruiting children from 3-year groups (years 3, 4, 5) with an average 27.8 pupils per class (based on 2018 KS2 figures from English schools), and an average 1.34 classes per year (based on the data from our UK KiVa pilot study where half of recruited schools had more than one class per year).

Assuming 111 pupils in years 3 to 5, an ICC of 0.02, and for one school dropout per arm, (10% pupil dropout due to either 'right to object' or loss to follow-up, based on data from a small Welsh BIG Lottery funded pilot RCT with 20 schools, led by the Dartington Social Research Unit), an 18% rate of victimisation, and a relative reduction of 22%, a trial involving 116 schools (58 per arm) would provide 90% power at a 5% significance level (a total of 12,828 pupils). In the Dartington trial matched pupil survey and attendance data were collected by unfunded school staff. For approximately 2500 pupils, matched measures completion at one year, across teacher rated SDQ', pupil survey data and attendance varied between 75 – 92% (mean 87.5%). This has been reported to the BIG lottery and a paper reporting this trial is under review. Since this was achieved with minimal funding and reliance on teachers to supervise the pupil survey and match data across two academic years, we are confident that with pupil data collection being undertaken by research staff it will be feasible to achieve the 90% rate. If a higher rate of victimisation and a larger effect size akin to the Finnish KiVa study of 1.47 is observed within the recruited schools then the sample size required will be lower and we will have more than the 90% power, given all other parameters (ICC, dropout) are held constant. 83% power can still be achieved if we find a smaller effect size akin to the pooled odds ratio of 1.24 (as per Ttofi et al.'s meta-analysis [6]) and the ICC is smaller at 0.01.

14.4 Missing, unused & spurious data

To investigate the impact of any missing outcome data on the trial conclusions, missing mechanisms will be explored, and appropriate imputation methods applied via sensitivity analyses. We will compare baseline characteristics and post-randomisation variables of pupils who have and have not completed primary outcome data. Multiple imputation will be performed to assess the impact of missing outcome data using the mi command in Stata. Imputation models will include outcomes (including pupil attendance), intervention arm, stratifying variables, and a main school effect to allow for clustering, as well as any appropriate baseline covariates. The main analyses will be repeated on the imputed datasets. As an added sensitivity analysis, a scenario-based imputation will be carried out such as best-worst case scenario assuming all lost to follow-up in the KiVa arm have been victimised and vice versa. Further details will be included in the statistical analysis plan (SAP), written prior to analysis.

14.5 Procedures for reporting deviation(s) from the original SAP

These will be submitted as substantial amendments where applicable and recorded in subsequent versions of the protocol and SAP.

14.6 Inclusion in analysis

Missing outcome data will not be replaced, and all main statistical analysis will be conducted on complete cases i.e. participants that provided data at baseline and 12 months.

15 Analysis

15.1 Main analysis

A detailed SAP will be written prior to analysis. The reporting of findings will be in accordance with the CONSORT guidelines for cluster RCTs and SPIRIT recommendations for reporting trials of interventions. Statistical analysis will be performed in R or Stata (version 13 or higher).

All analyses will be intention to treat (i.e. pupils will be analysed in the groups to which they were randomised, regardless of adherence to intervention) and missing outcome data will not be replaced (all main statistical analysis will be conducted on complete cases). Between-group comparisons will be presented with two-sided 95% confidence intervals (CIs). As the trial includes a reasonable number of

clusters, the analysis will be based on the individual pupil, allowing for clustering between pupils within school using robust standard errors. Analyses will control for the school level stratification variables (geographical area, school size, proportion of children eligible for FSM) and pupil characteristics (age, gender).

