3.2.3 Methods

Before the start of the 2020/21 academic year, KS2 pupils will complete questionnaires about their experience of bullying at school, how they feel about school and their general wellbeing. KS2 teachers will complete questionnaires about the behaviour of each pupil in their class, their confidence in dealing with bullying and the mental wellbeing. Pupils and teachers will complete these questionnaires towards the end of the 2020/21 academic year (May/June 2021). The study will be reporting whether there is a

reduction in the proportion of pupil self-reported bullying victimisation from the start to the end of the academic year and whether this reduction is greater within schools that delivered KiVa compared to schools that continued with their usual practice. To learn more about how KiVa lessons were delivered, the factors that influenced delivery, how it was delivered schoolwide and how it was received by participants, researchers will conduct interviews and focus groups with staff, pupils and parents in schools that delivered KiVa. Interviews will also be conducted with school staff from the control group to learn more about usual antibullying practices in UK primary schools. In addition, the cost of KiVa will be calculated and weighed up against any benefits in terms of reduced reported bullying, pupil quality of life and use of services related to bullying.

Trial findings will be disseminated through policy briefings, in press-releases, social media updates, via the creation of short audio-visual clips for schools and children and published in peer-reviewed academic journals and conference presentations.

4 Background

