Bullying in childhood is one of the most tractable public mental health problems facing young people [13-14]. Bullying is generally defined as a pattern of 'unwanted, aggressive behaviour ... that involves a real or perceived imbalance of power' [15]. The psychiatric morbidity arising from bullying is substantial; population studies suggest that 25-40% of mental health problems including depression, anxiety and selfharm in young adults may be attributable to childhood bullying [2-4]. Young people who are bullied are more likely to use mental health services in childhood and adolescence (odds ratio (OR) 2.53) and experience poor mental health up to age 50 (OR 1.30) [5]. During childhood, their use of school health services, primary care and specialist mental health service is increased. Bullying may also lead to school refusal and absenteeism [16] which can have serious impacts on educational attainment and employment prospects. Bullying perpetration also has negative impacts and is linked to later antisocial and violent behaviour and illegal drug use [6-7]. Thus, interventions that reduce bullying in schools can improve school attendance and behavioural problems and have the potential to substantially improve mental health and reduce depression, anxiety and self-harm in both childhood and adulthood.

UK school approaches to bullying vary widely and are rarely evidence based [17]. There is an urgent need to identify and scale up effective interventions across local and national school networks to address

bullying in schools, particularly in the early school years. This is also recognised by the Welsh Government as part of a national priority to improve levels of wellbeing in schools by Wales [18].

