5.4 Primary outcome measures

The primary outcome is the proportion of pupils self-reporting bullying victimisation and will be measured using the OBVQ [25]. In both the intervention and UP arms at Baseline and at 12 Month follow-up. This questionnaire measures the rate of total and different forms of bullying, including verbal, physical, relational and cyber-bullying. The OBVQ [25] has been used both in Finland and internationally for KiVa trials, enabling comparison across trials. The item that will be used to assess the primary objective is item 4, "How often have you been bullied at school in the past couple of months?" to which pupils may select one of the following responses: "I haven't been bullied at school in the past couple of month = 0", "it has only happened once or twice = 1", "2 or 3 times a month = 2", "about once a week = 3" or "several times a week = 4". The responses will be dichotomised so that a response of 2-4 will indicate bullying victimisation and responses 0-1 will indicate no bullying victimisation.

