15.1.1 Primary outcome

Multilevel logistic regression models will be used to compare the proportion of pupils reporting victimisation at 12 months by arm, and results presented as odds ratios and 95% CIs. Intra-cluster correlations (ICCs) alongside 95% CIs will also be reported.

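### The primary model omits baseline victimisation, which is collected before randomisation, yet the analysis set excludes pupils who lack it; precision is forgone, but the comparison is not biased and planned power stands

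*Protocol*

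**What the plan says.** Section 5.4 measures the primary outcome with one Olweus item, dichotomised, "In both the intervention and UP arms at Baseline and at 12 Month follow-up". Sections 10.2 and 14.2 and Table 1 place the baseline survey before randomisation. Section 14.1 says schools learn their allocation only once baseline data are in.

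On the model, section 15.1 states: "Analyses will control for the school level stratification variables (geographical area, school size, proportion of children eligible for FSM) and pupil characteristics (age, gender". Section 15.1.1 continues: "Multilevel logistic regression models will be used to compare the proportion of pupils reporting victimisation at 12 months by arm". Neither names the pupil's baseline answer.

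On the analysis set, section 14.6 states that "all main statistical analysis will be conducted on complete cases i.e. participants that provided data at baseline and 12 months".

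Section 14.4 plans multiple imputation of missing outcomes as a sensitivity analysis. Its imputation models may include other suitable baseline covariates. Section 15.1 gives no such latitude for the main model.

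**The concern.** The two rules do not fit together. If the model has no baseline term, nothing in it requires a baseline record, yet pupils without one are dropped. If baseline data are thought necessary for inclusion, they should be used.

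Two things are at stake. The first is precision: earlier victimisation can be expected to predict later victimisation to some degree, and adjusting for a prognostic value measured before randomisation reduces the variance of the arm comparison. The second is chance imbalance. Schools are the randomised units, so the arms can differ at baseline by an amount that is not small beside the 4-point target difference. To the extent that victimisation persists, such a difference carries into an estimate that does not adjust for it.

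**Working it through.** **Inputs from the protocol (section 14.3):** 18% against 14%, 5% significance (taken as two-sided, as the confidence intervals in section 15.1 are), 90% power, ICC 0.02, 111 pupils per school, 10% pupil dropout, one school lost per arm, 58 schools per arm.

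**1. Reproduce the stated size.**
- Pupils per arm = (1.96 + 1.2816)² × (0.18×0.82 + 0.14×0.86) / 0.04² = 1,760, so 3,520 in total, as stated.
- Design effect = 1 + 110×0.02 = 3.2, and 3,520 × 3.2 = 11,264. Dividing by 0.9 gives 12,516, and by 111 gives 112.8 schools, so 57 per arm. One more per arm gives 58, or 116 in all, as stated.
- 116 × 111 = 12,876, against the stated 12,828 (0.4% apart).

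No baseline correlation enters this calculation.

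**2. Power of the model as written.** Take 57 schools per arm and 100 pupils per school (111 less 10%).
- Effective n per arm = 57×100 / (1 + 99×0.02) = 5,700 / 2.98 = 1,913.
- z = 0.04 / √(0.268/1,913) = 3.379, and 3.379 − 1.96 = 1.419, so power is 92.2%.

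**3. Power with baseline adjustment.** The protocol gives no baseline to follow-up correlations, so the values below are assumptions. The formula is a linear-scale approximation for a binary outcome: r = [m×ICC×ρ_school + (1−ICC)×ρ_pupil] / [1 + (m−1)×ICC] with m = 100, and the variance factor is 1 − r².

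| ρ_pupil | ρ_school | r | 1 − r² | Power, 18% vs 14% | Power, OR 1.24 |
|---|---|---|---|---|---|
| none | none | 0 | 1 | 92% | 69% |
| 0.2 | 0.3 | 0.27 | 0.93 | 94% | 73% |
| 0.3 | 0.5 | 0.43 | 0.81 | 96% | 78% |
| 0.4 | 0.7 | 0.60 | 0.64 | 99% | 87% |

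The last column uses the smaller odds ratio that section 14.3 itself considers (18% against 15.04%), but at ICC 0.02. The protocol's 83% for that odds ratio assumes ICC 0.01.

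**4. Size of chance imbalance.** With an 18% rate and effective n of 1,913 per arm, the standard error of the between-arm difference in baseline victimisation is √(2×0.1476/1,913) = 1.24 points. The 95% range is about ±2.4 points before any gain from stratification.

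**5. Cost of the exclusion alone.** If a further 5, 10 or 20% of followed-up pupils lacked a baseline (assumed), pupils per school fall from 100 to 95, 90 or 80. Effective n becomes 1,880, 1,845 or 1,767, and power is about 92, 91 or 90%.

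**6. Does the exclusion bias the comparison?** A simulation used 600 trials, 57 schools per arm and 100 pupils each. About 15% of baselines were missing, with missingness tied to vulnerability but not to arm.
- With no true effect, the complete-case difference averaged 0.0004 (Monte Carlo standard error 0.0004), so no bias was seen.
- With a true effect, the risk difference was −0.036 in the subset and −0.041 in all pupils. The excluded pupils are at higher risk, so the subset describes a somewhat different population. That is not a spurious arm difference.

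**The case against.** The strongest reply is that nothing is broken. The planned power does not rely on the covariate, and stratification on area, size and free-school-meal eligibility already limits imbalance. Section 15.1 promises a detailed analysis plan, which could name the covariate. Requiring a baseline record also keeps out pupils who join after allocation. All of this stands as a limit on the point. It does not remove it: section 15.1 gives a specific covariate list and section 14.6 a specific analysis set, so an analysis plan that follows them inherits the mismatch.

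A reader might infer several stronger things that the documents do not support.

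- *That the exclusion biases the result.* The Background says "Bullying may also lead to school refusal and absenteeism", so pupils without a baseline may well differ from the rest. But baseline comes before randomisation and before schools learn their arm. For pupils enrolled then, a missing baseline cannot depend on arm.
- *That the trial is underpowered.* Steps 1 and 2 show otherwise. Power is lower only relative to an adjusted model, and by how much depends on assumed correlations.
- *That 10 to 20% of pupils will be discarded.* The 90% and 80% figures in section 9.3.1 are progression thresholds, not forecasts. The 10% dropout allowance in section 14.3 is supported by matched completion at one year, so it already covers much of this loss.
- *That every pupil has a baseline.* Parents may object and pupils may decline or be absent.
- *That the model fails the lay question.* Section 3.2.3 asks "whether this reduction is greater within schools that delivered KiVa compared to schools that continued with their usual practice". Under randomisation, comparing 12-month proportions has the same expected arm contrast as comparing change. An adjusted model also compares 12-month outcomes.

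**Conclusion.** The point holds as one of efficiency and internal consistency. The protocol excludes pupils for lacking a value that its stated model never uses, and leaves unused a covariate that it already pays to collect. The main cost is forgone precision: a variance factor of about 0.93 to 0.64, and power of about 94 to 99% instead of about 92%. These figures rest on assumed correlations and a linear-scale approximation. The exclusion itself costs about half a point to two points of power if 5 to 20% more pupils lack a baseline, and narrows the population described. The gain from adjustment matters most if the effect is smaller than planned. Validity of the randomised comparison and the planned 90% power are not in question.

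**What to change.** In sections 15.1 and 15.1.1, add the pupil's baseline Olweus victimisation to the primary model. Add the matching baseline score to each secondary model where one is collected.

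In section 14.6, define the primary set as pupils enrolled in the cohort before randomisation who have a 12-month outcome. Keep those with a missing baseline by a missing-indicator category or by imputing the baseline value, and state which. Say explicitly that pupils who join after allocation are excluded, so that the missing-baseline category does not readmit them.

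The cost is a few sentences, with no new data and no extra pupils. There is one small downside: the adjusted odds ratio is conditional on baseline and is not directly the 1.35 used for sizing. The report should say so.
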